### ***20.6 Responses at Week 96***

A complete/nearly complete response at week 96 was considered median-term efficacy. The digital photographs of the target hemangioma were assessed by centralized evaluation at West China Hospital of Sichuan University. Three trained investigators who were unknown of the study-group assignments independently evaluated the digital photographs taken at baseline and week 96 after the initial treatment. For more details regarding the procedures for median-term efficacy, refer to the **Collection and Assessment of Series Digital Photographs** section.

## **21 Safety assessments**

### ***21.1 In-house monitoring***

All patients were monitored as in-house patients for 8 hours with hourly measurements of cardiovascular examination at day 0 (week 0) and day 7 (week 1). Continuous bedside monitoring was performed on all infants during hospitalization by using a noninvasive multiparameter monitor. Blood pressure and heart rate were obtained before (baseline) and at 1, 2, 3, 4 and 6 hours following the first dose of  $\beta$ -blocker therapy. The blood glucose level was measured by fingerstick using an automated glucometer and obtained before (baseline) and at 4 hours after the first dose of propranolol or atenolol during hospitalization. These values were also recorded before and following the first dose of  $\beta$ -blocker on day 7 (week 1) after dose escalation. Blood pressure and heart rate values were compared with age-related reference ranges.

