**16 Study visits**

Study visits were scheduled at enrolment; at 1, 4, 12, and 24 weeks after treatment; and then every 12 weeks until the end of the study or if there was any specific need after enrolment. Body weight, height, heart rate, blood pressure, blood glucose, full blood count, liver function tests, renal function and ECG were obtained during protocol visits and in-between periods if needed. All adverse events, which were identified by the investigators as at least possibly treatment-related during the 24-week treatment phase, were collected by the investigator. At each visit, the drug will be handed over to the parent/guardian in an amount sufficient to last the interim duration.

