### ***21.2 Outpatient monitoring***

The patients' parents or guardians were asked to inform the investigators about adverse events at any time to ensure that potential adverse events could be handled promptly and appropriately. Parents or guardians were also provided with a patient booklet to record any possible adverse events during treatment. Data on adverse events was obtained at scheduled or unscheduled study visits based on information spontaneously provided by the subject and/or through questioning of the participant. Each scheduled visit included an evaluation of efficacy and routine examination. Routine examinations included physical examination, electrocardiography, routine blood tests, and blood glucose measurement.

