### ***21.3 Collection and management of adverse events***

The frequency of adverse events (e.g., sleep disturbance, cool or mottled extremities, diarrhea, etc.) were collected by the investigator and reported by parents. The investigators collected any untoward medical occurrence in the form of signs, symptoms, abnormal laboratory findings, or diseases that emerged or worsened relative to baseline assessment. All adverse events that were identified by the investigators as at least possibly treatment-related (treatment-emergent adverse events or adverse events that have worsened since baseline) were included in the analysis. For each adverse event, the percentage of subjects who experienced at least 1

---

occurrence of the given event was summarized by treatment group. Adverse events during the initial 24-week treatment phase were compared between the two groups.

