#### ***21.5 Relationship of adverse events***

All adverse events were collected and graded according to Common Terminology Criteria for Adverse Events, version 4.0 (CTCAE v4.0). The investigators evaluated each adverse event that occurred after administration of  $\beta$ -blockers regarding the relationship with the administration of  $\beta$ -blockers. The causality of the adverse event was determined by the investigators and classified as definitively not related,

---

probably not related, possibly related, probably related, or definitively related. Only patients with events that were at least possibly treatment-related were taken into consideration:

(1) Definitively not related: only a remote connection exists between the administration of  $\beta$ -blocker and the reported adverse event. Other conditions, including concurrent illness, progression or expression of the disease state or reaction of the concomitant medication, appear to explain the reported adverse event.

(2) Most likely, not related: an adverse event that does not follow a reasonable temporal sequence related to the administration of  $\beta$ -blocker and is likely to have been produced by the patient's clinical state, other modes of treatment or other known etiology.

(3) Possible related: an adverse event that has a reasonable possibility that the event may have been caused by the administration of  $\beta$ -blocker. The adverse event has a timely relationship to the administration of  $\beta$ -blockers. However, the pattern of response is atypical, and an alternative cause seemed more likely, or there is significant uncertainty about the cause of the event.

(4) Probable related: an adverse event that has a reasonable possibility that the event is likely to have been caused by the administration of  $\beta$ -blocker. The adverse event has a timely relationship and follows a known pattern of response, but a potential alternative cause may be presented.

(5) Definitely related: there is a reasonable possibility that the event might have been caused by the administration of  $\beta$ -blocker. A certain event has a strong temporal relationship, and an alternative cause is unlikely.

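### Isolated low glucose readings can drop out of the between-arm safety comparison through an unmasked causality judgement; one all-causality table in Section 25.5 would show how many

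*Combined protocol and SAP*

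**What the plan says.** Section 5 names hypoglycemia among the rare but possibly life-threatening effects of propranolol, traces it to beta-2 blockade, and offers the more selective atenolol as a way to reduce some side effects.

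Glucose is measured on a schedule. In Section 21.1, for day 0: "The blood glucose level was measured by fingerstick using an automated glucometer and obtained before (baseline) and at 4 hours after the first dose". For day 7, after escalation: "These values were also recorded before and following the first dose of" the drug. In Section 21.2, for visits: "Routine examinations included physical examination, electrocardiography, routine blood tests, and blood glucose measurement".

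The adverse event analysis is restricted by causality in three places:

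- Section 16 describes adverse events as those "identified by the investigators as at least possibly treatment-related during the 24-week treatment phase, were collected by the investigator".
- Section 21.3 includes in the analysis "All adverse events that were identified by the investigators as at least possibly treatment-related", with a bracketed gloss, "treatment-emergent adverse events or adverse events that have worsened since baseline". It then compares the arms over the first 24 weeks.
- Section 21.5 says "Only patients with events that were at least possibly treatment-related were taken into consideration".

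The investigators make that judgement (Section 21.5). The trial is open-label and only outcome assessors are masked (Section 6). The regimens also differ visibly, three doses a day against one (Section 17.1). Section 21.4 prints on-study limits for blood pressure and heart rate but not for glucose; 40 mg/dL appears only as an exclusion limit (Section 11(1)). Section 25.5 plans no summary of glucose values.

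**The concern.** A measured low value is objective, whereas whether it counts in the comparison is a judgement made with knowledge of the drug. Someone who expects hypoglycemia from a nonselective beta-blocker may attribute a low reading more readily to propranolol; someone wary of the less familiar drug may do the opposite. Either habit changes the counts without any change in the infants. Uniform under-attribution loses events and power instead.

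At stake is one descriptive safety comparison that bears on a stated reason for the trial. As planned, a reader could not see how many low readings the filter removed in each arm. The primary efficacy outcome is read from photographs by masked assessors and is not touched.

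**Working it through.** **1. Which readings are exposed.** Scheduled readings after the first dose, up to week 24, taking the week-1 visit as the day-7 admission: day 0 at 4 h (1) + day 7 before and after the dose (2) + weeks 4, 12 and 24 (3) = 6 per infant. The readings just after a dose on days 0 and 7 have an obvious time link to the drug and would probably be called possibly related. The visit readings at weeks 4, 12 and 24, or any reading during an intercurrent illness, are easier to assign to another cause.

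**2. Which routes bypass the filter.** Section 21.8 makes termination mandatory for recurrent or persistent hypoglycemia and sets no relatedness condition. Section 25.5 lists all premature discontinuations with treatment group, time and reason. Section 21.7 has interruptions recorded. What remains exposed is mainly the isolated low reading.

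**3. Size.** The documents give no hypoglycemia rate and no share of events judged related, so every rate and share below is an assumption. Arm size is 180 (Section 12), taken as the safety population. Section 25.4 names Fisher's exact and chi-square tests for categorical secondary outcomes and Section 25.5 names no test, so both are shown. Results come from enumerating all binomial outcomes at two-sided 5%, with uncorrected chi-square.

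*Bias.* With the same true rate p in both arms and shares fP (propranolol) and fA (atenolol) judged related, the observed rates are p·fP and p·fA. The spurious difference is p·(fP − fA); for example 0.02 × (0.90 − 0.50) = 0.008, or 0.8 points. The last two columns give the chance of a false significant result favoring atenolol, Fisher / chi-square.

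| fP / fA | Difference, p = 2% | Difference, p = 5% | False result, p = 2% | False result, p = 5% |
|---|---|---|---|---|
| 100 / 100% | 0 | 0 | 0.8 / 2.3% | 1.4 / 2.4% |
| 100 / 90% | 0.2 | 0.5 | 1.0 / 3.1% | 2.3 / 4.0% |
| 100 / 75% | 0.5 | 1.25 | 1.6 / 4.8% | 4.8 / 8.1% |
| 90 / 50% | 0.8 | 2.0 | 2.3 / 8.2% | 10.4 / 17.1% |

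Swapping the shares between arms gives the same figures against atenolol. By Fisher, the nominal one-sided 2.5% is exceeded only at the 5% rate with a gap of 25 points or more.

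*Power.* Propranolol rate against 0 on atenolol, with the same share judged related throughout (Fisher / chi-square, %):

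| True rate | 100% related | 90% | 75% | 50% |
|---|---|---|---|---|
| 2% | 15 / 49 | 11 / 41 | 6 / 29 | 1 / 11 |
| 3% | 45 / 79 | 36 / 72 | 22 / 58 | 6 / 29 |
| 5% | 89 / 98 | 82 / 96 | 67 / 91 | 30 / 66 |

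At 1% with no loss, power is 1 / 11%. With no events on atenolol, significance needs 6 on propranolol by Fisher (p = 0.030) or 4 by chi-square (p = 0.044).

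*Precision of the proposed table.* For 4/180 against 0/180, the difference is 2.2 points, Newcombe 95% CI −0.3 to 5.6.

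**The case against.** The filter may be nearly empty for this event. Section 21.5 counts an event as possibly related even when "an alternative cause seemed more likely, or there is significant uncertainty about the cause of the event", provided the timing fits. The gloss in Section 21.3 reads largely as a timing test, and Section 5 itself supplies a drug mechanism. Abnormal laboratory findings are collected (Section 21.3), Section 21.4 defines adverse events regardless of relationship, and CTCAE v4.0 supplies severity grades by reference (Sections 21.5 and 21.6). Hypoglycemia is one reason among several for the trial, and Section 5 gives more weight to central nervous system effects. If events are rare, the comparison is inconclusive with or without the filter.

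Most of this stands and limits the point to a minor one. It does not remove it. Section 21.5 sets out a five-level causality scale and excludes the two lowest levels, which is more than a timing test. CTCAE grading applies to events already recognized, and those events still face the filter. That raw values are collected means a count could be made, not that one is planned.

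Two stronger readings are tempting. A reader might infer that the plan tilts the safety result toward atenolol; nothing in the documents shows that attribution would differ by arm, or in which direction. A reader might also infer that hypoglycemia can vanish from the report; Sections 21.8 and 25.5 together should show recurrent or persistent cases by arm.

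**Conclusion.** The point holds in a narrow form and is minor. The between-arm comparison can lose isolated low glucose readings through a causality judgement made with knowledge of the drug, and the plan has no table that would reveal the loss. The size is unknown but probably small: under the assumed inputs, at most 0.8 points of spurious difference at a 2% rate and 2.0 points at 5%, the latter needing both a less rare event and a wide attribution gap. The direction cannot be known from the documents. This rests on the assumed rates and shares, on 180 infants per arm in the safety population, and on Section 21.8 being applied as written, without a relatedness test. The primary conclusion does not change.

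**What to change.** In Section 25.5 add one descriptive table by arm, regardless of causality:

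- the number and percentage of safety-population infants with any scheduled glucose reading after the first dose and up to week 24 below a limit fixed in advance (for example the protocol's own 40 mg/dL from Section 11(1));
- the number of infants with at least one such reading available;
- a 95% confidence interval for the difference;
- how many of the infants with a low reading also appear as a treatment-related hypoglycemia event, so that the loss through the filter is visible in each arm.

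Keep the existing adverse event table, because lows at home between visits can appear only there.

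The cost is a few lines of SAP wording and one table from data already collected, with no new procedure and no change in sample size. The downsides are one more descriptive comparison, likely inconclusive if the propranolol rate is about 1–2%, and a limit that is borrowed from enrollment and so must be justified in advance. Scheduled readings are also few, and Section 21.7 asks for dosing within 30 minutes of a feed, so they may miss lows that occur away from feeds.

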### ***21.2 Outpatient monitoring***

The patients' parents or guardians were asked to inform the investigators about adverse events at any time to ensure that potential adverse events could be handled promptly and appropriately. Parents or guardians were also provided with a patient booklet to record any possible adverse events during treatment. Data on adverse events was obtained at scheduled or unscheduled study visits based on information spontaneously provided by the subject and/or through questioning of the participant. Each scheduled visit included an evaluation of efficacy and routine examination. Routine examinations included physical examination, electrocardiography, routine blood tests, and blood glucose measurement.

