## 5 Study background and rationale

IHs are the most common tumors of childhood and occur in approximately 4% to 5% of infants. In the majority of cases, IHs are self-limited and resolve spontaneously without threat or complications. However, in approximately 10% of patients, the lesions can be disfiguring (e.g., facial involvement), destructive (e.g., ulceration), functionally significant (e.g., visual impairment), or even life-threatening (e.g., airway obstruction).

Currently, propranolol is the preferred treatment for problematic proliferating IHs. Although propranolol is clearly efficacious, rare adverse effects, such as hypoglycemia and bronchial hyperreactivity, may be life-threatening. Nonselective  $\beta$ -adrenergic antagonists, such as propranolol, are competitive antagonists of catecholamines at the  $\beta_1$ - and  $\beta_2$ -adrenergic receptors (ARs).  $\beta_2$ -AR blockade may result in hypoglycemia as a result of decreased glycogenolysis, gluconeogenesis, and lipolysis. Moreover, bronchial hyperreactivity is a direct effect of propranolol that results in bronchospasms due to pulmonic  $\beta_2$ -AR blockade. In addition, the lipophilic nature of propranolol is also important. When given to infants, the long-term effects of propranolol may affect the developing central nervous system (CNS), specifically learning and memory.

A solution to minimize some of the side effects of propranolol may be the use of more selective  $\beta_1$ -AR blockers, such as atenolol, which, at low dosages, have little  $\beta_2$  activity. More importantly, atenolol is a large, hydrophilic compound and may exhibit fewer CNS-related adverse effects (e.g., sleep disturbance and agitation) in the treatment of IHs. Unfortunately, there is a paucity of clinical data comparing the efficacy and safety of propranolol and atenolol.

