**6 Overall study design:**

This study is a prospective, multicenter, randomized, controlled, open-label clinical trial comparing propranolol and atenolol for the management of problematic IHs. Only patients who had never received IH-specific treatments and had normal heart, liver and renal functions were included. In both groups, patients were admitted and checked for side effects for 8 hours on day 0 and day 7. The patients were observed for therapeutic effects as outpatients during schedule visits. While comparing the efficacy of medication between propranolol and atenolol, the side effects of both drugs were also monitored.

---

Study Type    Interventional

Study Design    Allocation: Randomized

                  Endpoint Classification: Efficacy/Safety Study

                  Intervention Model: Parallel Assignment

                  Masking: Single Blind (Outcome Assessors)

                  Primary Purpose: Treatment; Efficacy/Safety assessment

---

---

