## **18 Collection and assessment of series of digital photographs**

Digital photographs of each target hemangioma were acquired by the site investigators at baseline and at 1, 4, 12, 24 and 96 weeks after treatment. The detailed procedures are listed below:

(1) The investigators used a unified camera model. The acquisition procedures ensured consistency in lighting, exposure and distance from the camera. All digital photographs were obtained using digital single-lens reflex cameras (Nikon D7000 or Nikon D7100, Nikon Inc., Melville, NY).

(2) For each participant site, the series images were taken in the same room. The room was a naturally well-lit room. The acquisition of digital photographs was performed carefully to avoid glare and direct light deep into the room.

(3) The background behind the patient when the images are acquired was either the parent's (or guardian's) chest or shoulder or an examination couch. The parents and patients wore light-color, nonreflective clothes. Similarly, the examination couch was covered with a light blue, non-reflective bed sheet.

(4) For each patient, at least one photograph (a front-on view with or without side-on view) was taken at each visit. If the patient had a mixed hemangioma, front-on view and side-on view photographs were taken (not mandatory).

(5) The quality of all the photographs was verified by site investigators before they were transferred to the CIS. If the photographs were not compliant with the acquisition protocol, repeated acquisition of the images was immediately performed.

(6) Each photograph was uploaded with the following information: patient ID number and date of photograph acquisition. The central investigators assessed the quality of the digital photograph once more.

(7) Digital photographs were independently assessed by three investigators (research assistants) working in the CIS who were unknown to the study group assignment and blinded to the clinical information. None of these investigators was involved in the clinical management of patients with IH. They were trained specifically to assess hemangioma evolution (response or nonresponse), hemangioma size and hemangioma color using a series of digital photographs.

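### Visit adverse events may rest on volunteered report or on questioning, with no common question set, so recorded rates of parent-observed symptoms (mainly sleep disturbance and agitation) could differ through unequal asking

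*Combined protocol and SAP*

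**What the plan says.** Section 21.2 (Outpatient monitoring) says that adverse event data at scheduled or unscheduled visits are obtained "based on information spontaneously provided by the subject and/or through questioning of the participant". Section 21.3 adds that events such as sleep disturbance, cool or mottled extremities and diarrhea "were collected by the investigator and reported by parents". No section makes questioning compulsory at a visit, fixes its wording or supplies a symptom list.

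Section 6 describes an "open-label clinical trial comparing propranolol and atenolol" in which only outcome assessors are masked. The masked role set out in Section 18 concerns images: "Digital photographs were independently assessed by three investigators (research assistants) working in the CIS who were unknown to the study group assignment". No masked role in collecting adverse events is described.

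Section 5 gives part of the reason for testing atenolol: it "may exhibit fewer CNS-related adverse effects", with sleep disturbance and agitation as the examples. Section 21.3 then compares adverse events between the arms over the first 24 weeks, as the percentage of subjects with one or more occurrences.

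Several provisions are not limited to one arm. Parents are asked to report events whenever they arise and receive a booklet to record them (21.2). They are taught warning signs before treatment (21.7). Heart rate, blood pressure, glucose, ECG and blood tests are scheduled (16, 21.1, 21.2).

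**The concern.** Whether an infant's disturbed sleep or agitation is recorded depends partly on whether anyone asks the parent. Under Section 21.2 a visit at which nobody asks still complies. When the people asking and answering know the drug, and the protocol states which drug should do better on these symptoms, asking can drift apart between arms.

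Efficacy is tested for noninferiority (Section 12) and the rationale for atenolol is fewer side effects (Section 5), so the tolerability comparison carries much of the trial's message. Section 21.6 also counts intolerable CNS effects as serious events, so capture of these symptoms feeds a serious-event category too. A difference produced by unequal asking could not be separated afterwards from a drug effect, because the plan does not call for a record of who was asked what.

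**Working it through.** **Inputs from the documents.** 180 per arm (Section 12; sized for the response endpoint and used here only as n). Two-sided 0.05 (Section 12). Endpoint: one or more occurrences over 24 weeks (21.3). Visits at weeks 1, 4, 12 and 24 (Section 16). The plan states no expected adverse event rate and no capture rate, so there is no figure of its own to reproduce.

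**Assumed inputs.** True incidence of a symptom 40% in both arms (20% as a variant). Capture at one contact 90% if the parent is asked and 50% if the event must be volunteered. Share of contacts at which the parent is asked: 90% on propranolol, and 60% or 40% on atenolol.

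**Step 1: capture at one contact,** with q the share asked: c = 0.9q + 0.5(1 − q).
- q = 0.9: 0.81 + 0.05 = 0.86
- q = 0.6: 0.54 + 0.20 = 0.74
- q = 0.4: 0.36 + 0.30 = 0.66

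**Step 2: recorded rate** when an event has k independent chances of capture: r = 0.40 × [1 − (1 − c)^k]. For k = 2: 0.40 × (1 − 0.14²) = 0.392; 0.40 × (1 − 0.26²) = 0.373; 0.40 × (1 − 0.34²) = 0.354.

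**Step 3: chance of a nominal two-sided P<0.05,** normal approximation. With gap d, pooled standard error s0 and unpooled s1, it is Φ[(d − 1.96·s0)/s1] + Φ[(−d − 1.96·s0)/s1]. Example, 34.4% v 29.6%: d = 0.048, s0 = √(2 × 0.32 × 0.68/180) = 0.0492, s1 = 0.0491, giving about 0.162 + 0.002 = 0.164.

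| Asked, propranolol v atenolol | Chances of capture | Recorded rates | Gap (points) | P<0.05 |
|---|---|---|---|---|
| 90% v 90% | any | equal | 0 | 5% |
| 90% v 60% | 1 | 34.4% v 29.6% | 4.8 | 16% |
| 90% v 60% | 2 | 39.2% v 37.3% | 1.9 | 7% |
| 90% v 60% | 3 | 39.9% v 39.3% | 0.6 | 5% |
| 90% v 40% | 1 | 34.4% v 26.4% | 8.0 | 38% |
| 90% v 40% | 2 | 39.2% v 35.4% | 3.8 | 12% |
| 90% v 40% | 3 | 39.9% v 38.4% | 1.5 | 6% |

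**Variants.** At 20% true incidence, one chance gives 10% and 18% for the two imbalances, and two chances give 6% and 7.5%. A milder imbalance, 90% v 75% asked with one chance, gives about 8% at 40% incidence and 6% at 20%. With 144 per arm (180 × 0.8, after the 20% dropout in Section 12), the one-chance figures of 16% and 38% become 14% and 31%.

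**Which rows apply.** A brief symptom seen between two visits is close to one chance. One that persists, or is remembered, across several of the four visits has more, and the gap shrinks quickly. If the chances are not independent, for instance because the same families are never asked, the result lies between the one-chance row and the row for that number of chances.

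**The case against.** The best defence is that the wording merely lists acceptable sources of an adverse event record and does not license staff to skip questions. On that reading good practice fills the gap, helped by the booklet, the open invitation to report, the pre-treatment teaching and the definitions of sleep disturbance and agitation in Section 21.4. These make 50% capture without questioning look low for some symptoms, and the gap depends on that figure. Moreover, much of the tolerability evidence does not depend on asking: monitored vital signs and glucose, ECG and blood tests, recorded dose changes (21.7) and discontinuations listed with reasons (25.5). Section 25.5 names no test or threshold for adverse events, so a false significant result is a yardstick here and not a planned decision.

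Most of this stands and limits the point. It does not answer it. The booklet and the invitation are still volunteered report, no prompts are described, and measurements do not capture sleep or agitation at home.

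A reader might infer that staff were given the choice of whom to ask, or that one arm was asked more. The text says neither: it sets no rule, which leaves the matter open. A reader might also extend the expected direction to diarrhea and other effects; Section 5 states it only for CNS effects.

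**Conclusion.** The concern holds in a limited form. Section 21.2 permits unequal asking in an unmasked setting, and the symptoms most exposed are those for which the protocol states an expectation. Measured events are little affected, and so is the primary response outcome, which masked assessors rate from photographs.

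The size is uncertain. On the assumed values, the chance of a nominal P<0.05 between equally tolerated drugs is about 16% with one chance of capture and 7% with two at 90% v 60% asked, and about 38% and 12% at 90% v 40%. Reading 16% or 38% as the error rate of the planned comparison would go too far: those figures need a single chance of capture, whereas the endpoint counts any occurrence over 24 weeks. The numbers illustrate a mechanism and do not forecast a result.

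It would also be too strong to say that uniform asking restores 5%. That row assumes equal asking gives equal capture. Parents who know the drug may answer the same question differently. Investigators who know it still decide what enters the analysis, since Section 21.3 includes "All adverse events that were identified by the investigators as at least possibly treatment-related".

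**What to change.** At weeks 1, 4, 12 and 24, ask every parent in both arms the same short scripted list of parent-observable effects that the protocol already names: for example sleep disturbance, agitation, cool or mottled extremities, diarrhea and breathing difficulty. Record each answer, including negative ones. Base the between-arm comparison of those effects on the scripted answers, and tabulate volunteered and unscheduled reports separately so that nothing is lost.

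The cost is a one-page form and a few minutes at visits that already exist. More mild events will be recorded in both arms. The change touches no dose, schedule or clinical rule.

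The safety section should also acknowledge that a script equalizes asking only; bias from open-label answering and from unmasked causality judgement remains. Where visits have already taken place without a script, the missing answers cannot be recovered, and the report should describe how events were elicited and treat differences in parent-reported symptoms with corresponding caution.
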